- Mitral isthmus (see Section 8.4.7)
- CTI (see Section 8.4.8)

At the investigator's discretion, use pacing maneuvers to determine the immediate effect of the ArcticLine ablation(s). Note: Direct Current (DCCV) or pharmacological cardioversion may be considered at any point during the procedure when restoration of sinus rhythm (SR) will assist in assessing the effectiveness of cryoablations or deemed necessary for the benefit of the patient.

Repeat ArcticLine ablation(s), as necessary to achieve conduction block, as described in Sections 8.4.6-8.4.8.

Upon completion of a minimum 30-minute wait time from the last ArcticLine ablation for each respective anatomy target, perform repeat voltage map of the left atrium using a 3D mapping system with the recommended settings. Use of 3-D mapping following the 30-minute waiting period should be performed while the subject is in Sinus Rhythm.

Notes:

- Reference ArcticLine Technical Guidance for recommendations on pacing maneuvers and 3D mapping settings.
- If Investigator is unable to successfully complete a lesion with the ArcticLine Catheter after a minimum of four (4) ArcticLine ablation applications, they may cross over to another FDA approved catheter. This will be considered an ArcticLine treatment failure.
- Temperatures of -80°C are expected with use of the ArcticLine Catheter.
- The ArcticLine Catheter ablation segment should be completely outside of the sheath prior to initiating an ablation. Freezing in the sheath may result in occluding the saline drip.
- Methods used to assess for conduction block must be documented and reported.
- Copies of voltage maps from ArcticLine procedures are to be sent to Medtronic.

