8.4.6. Linear Cryoablation with ArcticLine Catheter: Roof and Posterior Wall

Once confirmation all pulmonary veins have been isolated and the investigator determines the subject should move forward with ArcticLine ablation, perform the following steps:

Withdraw and remove the Arctic Front Advance catheter through the FlexCath Advance sheath.

Phrenic nerve monitoring must be done in accordance with Table 4. Insert and advance ArcticLine Catheter into the left atrium via the FlexCath Advance sheath and position as follows:

- Roof: Position the ArcticLine Catheter between the right and left superior pulmonary veins.
- Posterior wall: Position ArcticLine Catheter between the inferior pulmonary veins.

Repeat the following steps for both the roof and posterior wall locations:

- Assess the positioning and contact via fluoroscopy, ultrasound imaging, or other visualization technique. Reposition as needed.
- Perform the cryoablation. Cryoapplications of three (3) minutes is recommended for the roof and posterior wall targets in the left atrium.
- At the investigator's discretion, use pacing maneuvers to determine the immediate effect of the ArcticLine ablation(s).
- Note: It is the investigator's discretion to assess necessity of additional freezes to complete the desired ablation line.

Once the roof line and posterior wall lines are completed, assess the posterior wall for isolation using pacing maneuvers and/or 3D mapping.

If no further ArcticLine ablation(s) in the left atrium will be performed:

- Repeat voltage mapping of the left atrium using a 3D mapping system after a minimum 30-minute wait time from the last ArcticLine ablation for each respective anatomy target.
- Use of 3-D mapping following the 30-minute waiting period should be performed while the subject is in Sinus Rhythm.

Notes:

- The ArcticLine Catheter ablation segment should be completely outside of the sheath prior to initiating the ablation. Freezing in the sheath may result in occluding the saline drip.
- Upon the Investigator's assessment of procedure completion, Isoproterenol and/or adenosine may be used to further assess pulmonary vein conduction.
- Use of another catheter, other than the ArcticLine Catheter, for gap completion of the roof and/or posterior wall lines will be considered a treatment failure.

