8.4.7. Linear Cryoablation with ArcticLine Catheter: Mitral Isthmus

If the investigator chooses to perform a mitral isthmus line ablation, perform the following steps:

Advance the ArcticLine Catheter to the mitral isthmus by positioning between the mitral annulus and either posteriorly to the left inferior pulmonary vein or anteriorly to the left superior pulmonary vein. Phrenic nerve monitoring must be done in accordance with Table 4.

Assess the positioning and contact via fluoroscopy, ultrasound imaging, or other visualization technique. Reposition as needed.

Perform the cryoablation. Cryoapplications of three (3) minutes is recommended at the mitral isthmus.

- Note: It is the investigator's discretion to assess necessity of additional freezes to complete the desired ablation line.

Assess for bi-directional conduction block across the mitral isthmus, while subject is in sinus rhythm, using pacing maneuvers and/or 3D mapping following ArcticLine ablation.

- Note: Direct Current (DCCV) or pharmacological cardioversion should be performed prior to assessing patient for conduction block.

If no further ArcticLine ablations in the left atrium will be performed:

- Reconfirm bi-directional conduction block at the mitral isthmus following a 30 minute wait from the last ArcticLine ablation.
- Repeat voltage mapping of the left atrium using a 3D mapping system after a minimum 30-minute wait time for each respective ArcticLine lesion.

- Use of 3-D mapping following the 30-minute waiting period should be performed while the subject is in Sinus Rhythm.
- Local Activation Time (LAT) Mapping to further confirm conduction block following a 30-minute wait may be considered.

Notes:

- The ArcticLine Catheter ablation segment should be completely outside of the sheath prior to initiating the ablation. Freezing in the sheath may result in occluding the saline drip.
- Upon the Investigator's assessment of procedure completion, Isoproterenol and/or adenosine may be used.
- Use of another catheter, other than the ArcticLine Catheter, for gap completion of the mitral isthmus line will be considered a treatment failure.

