8.4.8. Linear Cryoablation with ArcticLine Catheter: Cavotricuspid Isthmus

If the investigator chooses to perform a CTI line ablation, perform the following steps:

Advance the ArcticLine Catheter to the CTI by positioning between the inferior vena cava and tricuspid annulus. Phrenic nerve monitoring must be done in accordance with Table 4.

Assess the positioning and contact via fluoroscopy, ultrasound imaging, or other technique. Reposition as needed.

Perform the cryoablation. Cryoapplications of four (4) minutes is recommended at the CTI.

- Note: It is the investigator's discretion to assess necessity of additional freezes to complete the desired ablation line.

Assess the CTI line for bi-directional conduction block using pacing maneuvers and/or 3D mapping following a 30-minute wait.

Notes:

- The ArcticLine Catheter ablation segment should be completely outside of the sheath prior to initiating the ablation. Freezing in the sheath may result in occluding the saline drip.
- Upon the Investigator's assessment of procedure completion, Isoproterenol and/or adenosine may be used.
- Use of another catheter, other than the ArcticLine Catheter, for gap completion of the cavotricuspid isthmus line will be considered a treatment failure.

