12.2. Ancillary Objective #1

Estimate the percentage of patients with acute treatment success of the ArcticLine Catheter at the left atrial roof and posterior wall in patients with demonstrated entrance block of all pulmonary veins and who underwent roof and posterior wall ablation with ArcticLine.

Endpoint Definition

Subjects must have confirmed block at the roof line and posterior wall line ("roof/wall") via periprocedural assessment of posterior wall isolation at the completion of the cryoablation procedure to be considered an acute treatment success.

Analysis Methods

The percentage of acute roof/wall treatment successes will be calculated as the number of roof/wall procedures achieving success divided by the number of index ArcticLine cryoablation procedures where the roof/wall was attempted. Exact methods will be used to construct a 95% confidence interval for the percentage.

Determination of Patients for Analysis

All subjects undergoing an ArcticLine cryoablation procedure of the roof/wall will be included. An ArcticLine cryoablation procedure of the roof/wall is considered to have occurred once an ArcticLine cryoapplication at the roof and/or wall begins. Only the first ArcticLine cryoablation procedure of the roof/wall per subject will be included.

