12.3. Ancillary Objective #2

Estimate the percentage of patients with acute treatment success of the ArcticLine Catheter at the mitral isthmus in patients who underwent mitral isthmus ablation with ArcticLine.

Endpoint Definition

Subjects must have confirmed bi-directional conduction block at the mitral isthmus line via periprocedural assessment at the completion of the cryoablation procedure to be considered an acute treatment success.

Analysis Methods

The percentage of acute mitral isthmus line treatment successes will be calculated as the number of mitral isthmus line procedures achieving success divided by the number of index ArcticLine cryoablation procedures where the mitral isthmus line was attempted. Exact methods will be used to construct a 95% confidence interval for the percentage.

Determination of Patients for Analysis

All subjects undergoing an ArcticLine cryoablation procedure of the mitral isthmus will be included. An ArcticLine cryoablation procedure of the mitral isthmus is considered to have occurred once an ArcticLine cryoapplication at the mitral isthmus begins. Only the first ArcticLine cryoablation procedure of the mitral isthmus per subject will be included.

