
Analysis Methods

The percentage of acute roof/wall treatment successes will be calculated as:

(the number of subjects with roof/wall index procedures achieving success)

divided by

(the number of subjects with index ArcticLine cryoablation procedures where a roof or wall ablation was attempted).

An attempted roof or wall ablation is considered to have occurred once an ArcticLine cryoapplication begins, as evidenced on the NON PVI ABLATION ENERGY APPLICATION CRF by a positive duration of application where the location is either "POSTERIOR WALL, LEFT ATRIUM" or "ROOF, LEFT ATRIUM":

Non PVI Ablation Energy Application

Application Sequence Number	Catheter Number	Location	Phrenic Nerve Monitoring Performed	Coldest Temperature (C)	Ablation Start Time	Duration of Ablation (seconds)
1		APCATLC_PRLOC / ABLATION LOCATION / 1	 CMAP  PACING OF RIGHT PHRENIC NERVE  PACING OF LEFT PHRENIC NERVE  PACE MAPPING			

To be included in the numerator, a subject must have posterior LA wall isolation at the roof line marked as 'YES' on the Procedure CRF:

Procedure Summary (Continued)

Was posterior LA Wall isolation achieved

NO YES PSLAISO_PROCCUR / NY /1

If No,

Was conduction block present at the roof line

NO YES CELKRF_PAOCUR /NY /1

The point estimate of the acute treatment success rate of roof/wall ablations will be reported along with its corresponding exact (Clopper-Pearson) 95% confidence interval.

Determination of Subjects for Analysis

All subjects with index ArcticLine cryoablation procedures where a roof or wall ablation was attempted will be included in this metric.

7.24 Ancillary Objective 2

Estimate the percentage of patients with acute treatment success of the ArcticLine Catheter at the mitral isthmus in patients who underwent mitral isthmus ablation with ArcticLine.

Ancillary Endpoint #2

Subjects must have confirmed bi-directional conduction block at the mitral isthmus line via periprocedural assessment at the completion of the cryoablation procedure to be considered an acute treatment success.

Analysis Methods

The percentage of acute mitral isthmus line treatment successes will be calculated as:

(the number of subjects with mitral line index procedures achieving success)

divided by

(the number of subjects with index ArcticLine cryoablation procedures where a mitral isthmus line was attempted).

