This includes any subject for whom the NON PVI ABLATION ENERGY APPLICATION CRF indicates a positive duration of application where the location is "MITRAL VALVE ISTHMUS OR LINE", or who has a value of "NO" or "YES" indicated in response to the Procedure CRF question "Was bi-directional mitral isthmus conduction block achieved?":

Was bi-directional mitral isthmus conduction block achieved

NO BIMICE_PROCCUR /
 YES BLOCK_ACHIEVED_CONFIRMED /1
 NOT APPLICABLE MI
ABLATION NOT PERFORMED

To be included in the numerator, a subject must have "YES" indicated in response to the same question.

The point estimate of the acute treatment success rate of mitral isthmus ablations will be reported along with its corresponding exact (Clopper-Pearson) 95% confidence interval.

Determination of Subjects for Analysis

All subjects with index ArcticLine cryoablation procedures where a mitral isthmus line was attempted will be included in this metric.

7.25 Ancillary Objective 3

Estimate the percentage of patients with acute treatment success of the ArcticLine Catheter at the CTI in patients who underwent CTI ablation with ArcticLine.

Ancillary Endpoint #3

Subjects must have confirmed bi-directional conduction block at the CTI line via periprocedural assessment at the completion of the cryoablation procedure to be considered an acute treatment success.

Analysis Methods

The percentage of acute CTI line treatment successes will be calculated as:

(the number of subjects with CTI line index procedures achieving success)

divided by

(the number of subjects with index ArcticLine cryoablation procedures where the CTI line was attempted).

The denominator includes any subject for whom the NON PVI ABLATION ENERGY APPLICATION CRF indicates a positive duration of application where the location is "CAVOTRICUSPID ISTHMUS" or any subject with a "NO" or "YES" response to the Procedure CRF question "Was bi-directional block confirmed at the cavo-tricuspid isthmus (CTI)?":

Was bi-directional block confirmed at the cavo-tricuspid isthmus (CTI)

- NO BICTICB PROCCUR /
- YES BLOCK ACHIEVED CONFIRMED
- NOT APPLICABLE, CTI ABLATION NOT PERFORMED

To be included in the numerator, a subject must have "YES" indicated in response to the same question. The point estimate of the acute CTI line ablation treatment success rate will be reported along with its corresponding exact (Clopper-Pearson) 95% confidence interval.

Determination of Subjects for Analysis

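### Ancillary Objectives 1–3 score acute success from final block alone, so a line finished with another catheter counts as an ArcticLine success although Protocol 8.4 calls it a treatment failure

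*SAP*

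**What the plan says.** **The failure rule.** Protocol 8.4.1 lets the investigator change to another catheter if a lesion cannot be completed after at least four ArcticLine applications, and adds: "This will be considered an ArcticLine treatment failure". The sections on each line repeat the rule for use of any other catheter:

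- 8.4.6: "for gap completion of the roof and/or posterior wall lines will be considered a treatment failure"
- 8.4.7: "for gap completion of the mitral isthmus line will be considered a treatment failure"
- 8.4.8: "for gap completion of the cavotricuspid isthmus line will be considered a treatment failure"

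**The endpoints.** Protocol 12.2 asks for block at the roof and posterior wall lines "via periprocedural assessment of posterior wall isolation at the completion of the cryoablation procedure to be considered an acute treatment success". Protocol 12.3 and 12.4 ask for bidirectional block at the mitral isthmus and CTI in the same way. None of the three mentions the catheter that achieved the block.

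**SAP numerators.** SAP 7.23 requires that "a subject must have posterior LA wall isolation at the roof line marked as" YES. SAP 7.24 and 7.25 require YES to the mitral or CTI block question.

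**Denominators.** Protocol 12.2–12.4 count a target as treated only once ArcticLine has been applied there. For the mitral line: "An ArcticLine cryoablation procedure of the mitral isthmus is considered to have occurred once an ArcticLine cryoapplication at the mitral isthmus begins". SAP 7.23 states the same principle, but its CRF evidence is any row of positive duration at the location. SAP 7.25 says: "The denominator includes any subject for whom the NON PVI ABLATION ENERGY APPLICATION CRF indicates a positive duration of application" at the CTI, and also admits anyone with a NO or YES to the block question. SAP 7.24 does the same for the mitral line. None of the three filters by catheter.

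**The concern.** Objectives 1–3 estimate acute success of the ArcticLine Catheter, and the study's stated use is to guide device design and a pivotal trial. SAP 7.6 and 7.8 also put these three objectives into the interim report, at FDA's request. If a crossover ended in block, the reported rate would describe what the whole procedure achieved with whatever catheters were used. It would hide the cases of most interest for device design, those in which ArcticLine could not finish the line, and it would contradict the protocol's own classification of them.

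**Working it through.** **1. Trace one case through both documents.** A subject receives four ArcticLine applications at the mitral isthmus without block. The investigator changes catheter and block is then confirmed.

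| Source | Test applied | Score |
|---|---|---|
| Protocol 8.4.1 | Crossover after at least four applications | Failure |
| Protocol 8.4.7 | Other catheter used for gap completion | Failure |
| Protocol 12.3 | Block at completion | Success |
| SAP 7.24 | Mitral application of positive duration, block question YES | Success |

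The roof/wall and CTI lines behave identically.

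**2. Does another endpoint apply the rule?** No. In SAP 7.26 (Objective 4) the only rule on other energy sources makes repeat ablation with radiofrequency a chronic failure. Crossover at the index procedure is not listed, and SAP 7.2.2 states that no repeat ablations have been or will be performed. If the 8.4 rule does not govern Objectives 1–3, it affects nothing.

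**3. Could the data identify these cases?** Yes. SAP 7.28 (Objective 6) uses the same Non-PVI Ablation Energy Application CRF, keeps rows whose catheter number maps to model 2AL35, and drops rows from radiofrequency catheters and Freezor MAX. The form can therefore hold rows from other catheters, and the filter exists.

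**4. Denominator evidence.** Take a CTI line made wholly with another catheter in a subject treated with ArcticLine elsewhere. Protocol 12.4 excludes it, because no ArcticLine application began at the CTI. The CRF evidence in SAP 7.25 admits it, and it scores as a success if block is YES.

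**5. Size.** The method is the planned exact (Clopper-Pearson) 95% interval for x successes in n:

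- lower limit = 2.5% quantile of Beta(x, n − x + 1)
- upper limit = 97.5% quantile of Beta(x + 1, n − x), or 1 when x = n

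Check against the SAP's only precision figure, a width of 32% for 1/15 in Section 6: the interval is 0.17% to 31.95%, width 31.8%, which rounds to 32%. It reproduces.

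Now suppose every line ends in block, but one of the n was finished by another catheter. The planned score is n/n, the 8.4 score is (n − 1)/n, and the difference is 1/n.

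| n | Scored as planned (95% CI) | Scored by Protocol 8.4 (95% CI) | Difference |
|---|---|---|---|
| 15 | 15/15 = 100% (78.2–100) | 14/15 = 93.3% (68.1–99.8) | 6.7 points |
| 10 | 10/10 = 100% (69.2–100) | 9/10 = 90% (55.5–99.7) | 10 points |
| 5 | 5/5 = 100% (47.8–100) | 4/5 = 80% (28.4–99.5) | 20 points |

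Here n = 15 is the planned number treated. The values 10 and 5 are assumed sizes for the mitral and CTI subsets, which need not include every subject. At n = 15, two crossovers would give 13/15 = 86.7% (59.5–98.3) and three 12/15 = 80.0% (51.9–95.7).

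**6. Related points on Objective 4 (minor).** A line finished by another catheter passes the acute-block entry criteria in SAP 7.26 unmarked. SAP 7.26 also adds confirmed CTI block as an entry criterion; Protocol 12.5 does not have it, and SAP 7.8 does not list it as a change.

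**The case against.** The best counter-arguments are these.

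- **The rule is not labelled acute.** Sections 8.4.6–8.4.8 say only treatment failure. But 8.4.1 ties the failure to ArcticLine and to completing a lesion during the procedure, which is what Objectives 1–3 measure, and no other endpoint uses the rule.
- **The endpoints refer to completion of the cryoablation procedure, so block obtained by radiofrequency might fall outside.** That phrase names the study procedure as a whole, and the reading would in any case fail for Freezor MAX, which is itself a cryocatheter.
- **The SAP follows Protocol 12.2–12.4 faithfully.** True. The gap starts in the protocol, and both documents need attention.
- **CRF completion instructions are not shown.** An instruction to answer NO after crossover would close the gap in practice. Neither document states one.
- **The denominator point is narrow.** This stands. SAP 7.23 does name an ArcticLine application as its principle, and a compliant crossover subject belongs in the denominator anyway. The loose evidence matters for a line made wholly with another catheter.
- **All procedures were complete by SAP version 3, so a scoring change would follow the outcomes.** This stands as a reason for disclosure. The change would apply a failure rule already in the protocol.
- **Scoring undocumented cases as failure resembles imputation.** It is consistent with the endpoint's requirement that block be confirmed.
- **These are descriptive ancillary estimates and the effect may be zero.** Both true. They limit the severity but do not make the scoring correct.

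**Conclusion.** The concern holds: the plan is wrong as written on this point and should be fixed. Followed literally, it reports as an acute ArcticLine success a line that Protocol 8.4 classes as a failure. Confidence in the contradiction is high, because it rests on the text. The size is unknown. It is 1/n per crossover that ended in block, so 6.7 points at n = 15 and more for a smaller mitral or CTI subset, and it is zero if there were none. The conclusion assumes that the 8.4 failure notes are meant for the acute endpoints and that no unseen CRF instruction already directs sites to answer NO after crossover.

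**What to change.** Reconcile Protocol 8.4 with 12.2–12.4, and state in SAP 7.23–7.25 how crossovers are scored:

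- **Denominator:** subjects with at least one application row at the target whose catheter number maps to the ArcticLine (2AL35).
- **Success:** block is YES and no other catheter was used to complete the line or close a gap at that target. Crossovers and gap completions stay in the denominator as failures.
- **Flagging:** use rows from any other catheter at the target to identify cases for review. A lesion added after ArcticLine block was already documented is not gap completion; if the record does not show this, score failure.
- **Reporting:** give the number flagged per target, including zero. List the change in SAP 7.8, noting that it was made after the procedures were complete.
- **Objective 4:** keep the population of Protocol 12.5 and identify subjects whose line was completed by another catheter. Remove the CTI-block criterion or list it in SAP 7.8.

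The cost is wording in both documents, one filter on a field already used for Objective 6, and a short review of flagged cases. The downside is that the acute success rates may look less favourable.

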Study Design	
The study is a prospective, interventional, multi-center, non-randomized, single arm, unblinded clinical study. Adult subjects with history of persistent atrial fibrillation (AF), including those with concomitant typical atrial flutter (AFL), to undergo ablation of:
 
 • Pulmonary veins (required, unless prior successful pulmonary vein isolation confirmed at start of study procedure), • Left atrial roof and posterior wall (required) • Mitral isthmus (optional, as determined by investigator), and • Cavo-tricuspid isthmus (required if subject has a history of AFL or AFL is induced during the study procedure, otherwise optional as determined by investigator). 
Study subjects from all participating geographies will be followed for 6 months after the index ArcticLine procedure and will be exited from the study at the conclusion of the 6 month follow-up visit.
 
Note: Safety and effectiveness data collected beyond the 6 month visit due to CIP Version 4 follow-up requirements will be adjudicated and included in the final report.

Sample Size	Up to 15 subjects will be treated with the ArcticLine Catheter
Inclusion/Exclusion Criteria	
Inclusion Criteria
 
 • Documentation of symptomatic persistent AF: 
 ○ Defined as having a continuous episode that is sustained beyond 7 days documented via consecutive ECG recordings, or ○ Defined as having a continuous episode that is sustained beyond 7 days documented by an ECG recording and one doctor note indicating the patient had symptoms consistent with AF • Age 18 through 80 years old • Failure or intolerance of at least one Class I or III antiarrhythmic drug • Subject is able and willing to consent to participate in the study and will commit to completion of all follow-up requirements 
Exclusion Criteria
 
 • Longstanding persistent AF, defined as continuous AF greater than 12 month duration • Left atrial diameter greater than 5.0 cm • Active systemic infection • History of thromboembolic event within the past 6 months or evidence of intracardiac thrombus at the time of the procedure

- Prior left atrial ablation attempt, with exception of:
 - Any pulmonary vein isolation attempt to treat AF, or
 - Successful ablation to treat Wolff-Parkinson White syndrome
- History of left atrial tachycardia

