8.8. Scheduled Follow-up Visits

After receiving notice of a completed study procedure, Medtronic will provide the target dates and windows for each visit to the center. Should a subject miss a visit or the visit fall outside the pre-specified window, a study deviation must be reported and the original follow-up schedule maintained for subsequent visits.

Data analyses include follow-up visits, regardless of whether the visit occurs within the window. Therefore, a late visit is preferred over a missed visit but must be accompanied by a deviation. Follow-up visit windows are listed in Table 5 and are based on days after the index ArcticLine Catheter ablation procedure.

Table 5: Follow-up Schedule

Occurrence/ Visit	Window (Calculated days after the ablation procedure)	
	Window Start	Window End
Enrollment/Baseline ¹	-30 days	Day 0
Index ArcticLine Procedure	Day 0	Day 0
1 week phone or office	7 days	14 days
3 month	91 days	105 days
6 month	165 days	179 days
¹ Note: If the time between the consent date and the procedure exceeds 30 days, the subject must be re-evaluated against inclusion and exclusion criteria to ensure they still qualify for the study.		

Multiple modes of data collections may be employed to support the collection of required visit data at the 3 and 6 month visits such as: In office patient clinic visit, direct to patient contact (i.e. telephone, email, mail contact, etc.), and remote technology transmissions/uploads.

The following information is required to be collected at the follow-up visits:

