8.8.3. Six Month Visit

- Review medications
- Adverse event assessment
- Review symptoms suggestive of recurrent AF/AT/AFL
- 12 lead ECG
- 24-hour continuous monitoring with Holter
- Collect or ensure return of ambulatory monitoring equipment

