The probability of a subject achieving effectiveness success at 6 months (182 days) will be estimated using survival analysis (the Kaplan-Meier method). The standard error will be approximated using Greenwood's formula. A two-sided 95% log-log confidence interval for the probability will be constructed.

For every treated subject, day 0 is defined as the day of the index ArcticLine procedure. For subjects without treatment failure through 6 months, those subjects will be censored at the last rhythm monitoring assessment (either in person monitoring at a visit via ECG/Holter, or through ambulatory ECG/transtelephonic monitoring). If a subject without a treatment failure is lost to follow-up, the censoring date will be set to the last date of rhythm monitoring that produced an interpretable rhythm; the date of capture/recording for a rhythm that the core lab was unable to interpret would not count.

For the AF/AT/AFL component of the endpoint, if documentation resulted from rhythm monitoring occurring at the 6-month visit within the 6-month visit window, the date of recurrence will be set to 182

days from the study ablation procedure so that these events will be counted as treatment failures in the 6-month Kaplan-Meier analysis.

Additionally, as stated in the CIP, standard statistics will be used to summarize the percentage of patients without AF/AFL/AT and cumulative time spent in AF/AFL/AT as collected from the 6 month Holter data. Listings will be provided for any data collected relevant to this objective that occurred after 6 months, due to CIP v5 follow-up requirements.

Determination of Subjects for Analysis

- All ArcticLine treated subjects who meet the following criteria will be included in the analysis:
 - o Confirmed acute entrance block of all pulmonary veins
 - o Confirmed acute posterior wall isolation (i.e. roof line and posterior wallline conduction block)
 - o Confirmed acute bi-directional conduction block at the mitral isthmus, if applicable
 - o Confirmed acute bi-directional conduction block at the CTI, if applicable
 - o Available 6 month Holter data (only required for description of Holter times, but not necessary for inclusion in Kaplan-Meier analysis)

7.27 Ancillary Objective 5

Estimate the incidence of ArcticLine Catheter-related and ArcticLine cryoablation procedure related serious adverse events (SAE) through the 6 month visit.

Ancillary Endpoint #5

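### Chronic-success Kaplan-Meier: failures found at the 6-month visit are moved to day 182 while event-free subjects are censored at the visit itself, so one such failure can drive the estimate to 0%

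*SAP*

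**What the plan says.** SAP 7.26 (Ancillary Objective 4, Analysis Methods) sets three rules:

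- **Time point.** "The probability of a subject achieving effectiveness success at 6 months (182 days) will be estimated using survival analysis", with a Greenwood standard error and a two-sided 95% log-log interval.
- **Failures found at the 6-month visit.** For the AF/AT/AFL component, if the documentation comes from monitoring "occurring at the 6-month visit within the 6-month visit window, the date of recurrence will be set to 182" days after the ablation. The reason given is to make these events count in the 6-month estimate.
- **Subjects without failure through 6 months.** "those subjects will be censored at the last rhythm monitoring assessment". Nothing moves them to day 182.

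The protocol fixes the timing. Table 5 in section 8.8 reads "6 month 165 days 179 days". At the six-month visit (8.8.3) the site must "Collect or ensure return of ambulatory monitoring equipment". According to the synopsis, subjects "will be exited from the study at the conclusion of the 6 month follow-up visit". Section 8.8 adds: "Data analyses include follow-up visits, regardless of whether the visit occurs within the window".

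Data collected after 6 months under the earlier follow-up schedule are to be listed. The SAP does not say whether they extend follow-up in the Kaplan-Meier analysis.

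**The concern.** A Kaplan-Meier estimate is valid only if those still at risk when an event is counted represent everyone who has not yet failed. Here two subjects seen on the same day, say day 172, are handled differently according to outcome. The one with AF stays in the risk set until day 182, and the one without AF leaves on day 172. By day 182 the risk set holds the failures and few or no successes.

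The re-dating serves no purpose for in-window visits, since an event on day 165 to 179 already falls before day 182. The case that does need a rule has none. AF first documented at a late 6-month visit, for example on day 185, is not re-dated and counts as event-free at day 182, although the endpoint runs through the 6-month visit and the protocol includes late visits in the analyses.

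Objective 4 is the study's only chronic effectiveness objective, and the study's data are meant to inform a future pivotal study. A figure wrong for mechanical reasons would go into that planning.

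**Working it through.** The documents give no expected value for this estimate, so there is no figure of the plan's own to reproduce on this point.

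**Inputs**
- Evaluation time: day 182 (SAP 7.26).
- 6-month window: day 165 to 179 (Protocol Table 5). The gap to day 182 is 182 − 179 = 3 to 182 − 165 = 17 days.
- Cohort: at most 15 (SAP 7.7). It may be smaller, because SAP 7.26 also requires confirmed acute block.
- Not in the documents: *m*, the number of event-free subjects whose counted rhythm monitoring reaches day 182 or later. It is shown as a range.

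**Formula.** Let *e* subjects fail earlier and *k* have their first failure documented at an in-window 6-month visit. Everyone else is event-free and attends that visit. Under the SAP rules the risk set at day 182 is *k* + *m*, so

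S(182) = (1 − e/15) × m/(k + m).

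With every event-free subject who completes the visit also placed at day 182, the estimate is (15 − e − k)/15.

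**One visit failure, none earlier (e = 0, k = 1)**

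| m | SAP rule, m/(1 + m) |
|---|---|
| 0 | 0% |
| 1 | 50.0% |
| 2 | 66.7% |
| 5 | 83.3% |
| 7 | 87.5% |
| 14 (all event-free subjects) | 93.3% |

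The sample proportion is 14/15 = 93.3%. At m = 0 the Greenwood term d/[r(r − d)] has r = d = 1 and is undefined, so there is no log-log interval. With common dating the result is 93.3% (95% log-log interval 61.3% to 99.0%). At m = 0 the SAP rule also gives 0% with two or three visit failures, and with 12 or 10 evaluable subjects.

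**Three earlier and two visit failures (e = 3, k = 2).** The first factor is 12/15 = 0.80.
- m = 0: 0.80 × 0/2 = 0%
- m = 2: 0.80 × 2/4 = 40%
- m = 5: 0.80 × 5/7 = 57%
- Common dating: 10/15 = 66.7%

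**How often this would occur.** Assume, for illustration only, that each of 15 subjects has a 20% chance of failing earlier and a 10% chance of first failing at the visit, so true success is 70%. At m = 0:
- The probability of at least one visit failure, which makes the estimate exactly 0%, is 1 − 0.9^15 = 79%.
- Without a visit failure, each subject's chance of being event-free is 0.70/0.90 = 0.778. The mean estimate is therefore 0.9^15 × 0.778 = 0.206 × 0.778 = 16%.

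Simulation under the same assumptions gives a mean of about 51–52% if a quarter of event-free subjects are monitored past day 182, and about 62% if half are.

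**Would actual dates for both groups be enough?** No. With 14 event-free subjects censored at day 170, a single failure on day 165 gives 14/15 = 93.3% and the same failure on day 179 gives 0%. In simulation, with visit days uniform over the window, the mean is about 56%. With both groups at day 182 it is 70%.

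**The case against.** The strongest reply has four parts.

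- **Later monitoring.** Before protocol version 5, follow-up ran to 12 months, and the documents expect some effectiveness data beyond 6 months. Censoring is at the last rhythm assessment, not at the visit as such, so some event-free subjects may still be at risk at day 182. This stands: the m = 0 results are the worst case. But the documents do not give the number of such subjects or say whether their later data count, and the estimate stays low unless all event-free subjects have them.
- **Conditional effect.** The rule acts only when an arrhythmia is first documented at an in-window 6-month visit. Earlier recurrences, drug failures and reablations keep their own dates, and with no visit-detected failure nothing changes. This also stands, but the 12-lead ECG and 24-hour Holter scheduled at that visit make such a finding an ordinary event.
- **Weight.** The objective is ancillary and descriptive, no hypothesis is tested, and a 6-month Holter percentage is reported alongside. True, but the Holter summary leaves out earlier recurrences, drug failures and reablation, so it cannot replace the composite.
- **The remedy.** Moving event-free subjects to day 182 credits them with 3 to 17 unobserved days, and late visits could be handled in other ways. Fair, but the SAP already moves failures by the same interval, and the endpoint is defined through the 6-month visit rather than a calendar day. How late a visit may count should be stated.

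**Conclusion.** The rule is wrong as written. Subjects assessed at the same visit are timed differently according to outcome, and nothing elsewhere in either document corrects this. If no event-free subject has counted monitoring on or after day 182, a single failure first found at an in-window 6-month visit turns 93.3% into 0% with no interval. With 2 or 5 such subjects the figure is 66.7% or 83.3%, and agreement with 93.3% needs all 14. These results assume 15 evaluable subjects, no loss before the visit and no earlier failure. The 16% mean and 79% frequency also rest on the illustrative failure rates and on m = 0. The primary safety objective is not affected. The late-visit gap is a smaller, separate fault in the same rule and works in the opposite direction.

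**What to change.** Replace the re-dating and censoring text in SAP 7.26 with two rules:

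1. Failures first documented at the 6-month visit are placed at day 182. Subjects with an interpretable 6-month rhythm assessment and no failure are censored at day 182, after events on that day. Both are assigned by nominal visit, so late 6-month visits are included, with a stated limit on how late a visit may be.
2. Censoring at the last interpretable rhythm is kept only for subjects with no 6-month assessment.

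The SAP should also say whether monitoring after the 6-month visit under the earlier schedule enters the Kaplan-Meier analysis or is only listed.

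The cost is two sentences and a small programming change, with no new data. SAP 7.8 already allows a revised SAP version for such a change.
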